## **2.5. Sequence of Planned Analyses**

### **2.5.1. Planned Interim Analyses**

An unblinded interim analysis is planned after the first 40-52 randomized patients have completed the treatment period, experienced LoAC, or withdrawn from the study completely. The main purposes of the interim analysis include sample size re-assessment and futility analysis. The details are in Section 13 and the Interim Analysis Charter.

### **2.5.2. Final Analyses and Reporting**

All final analyses identified in this SAP will be performed after the final database lock.

### **3. ANALYSIS SETS**

#### **3.1. Intent-to-Treat Analysis Set**

The intent-to-treat (ITT) analysis set will include all randomized patients and will be used as the population for the primary efficacy analysis.

In the ITT analysis set, treatment will be assigned based on the treatment to which patients were randomized, regardless of which treatment they actually received.

Data collected from patients after treatment discontinuation will be included in the ITT analysis set.

#### **3.2. Modified Intent-to-Treat Analysis Set**

The modified intent-to-treat (mITT) analysis set is a subset of the ITT analysis set including only patients who receive at least 1 dose of IMP.

The mITT analysis set will serve as the sensitive analysis.

#### **3.3. Safety Analysis Set**

The safety analysis set will include all randomized patients who receive at least 1 dose of IMP.

In the safety analysis set, treatment will be assigned based on the treatment patients actually received, regardless of the treatment to which they were randomized, unless otherwise specified.

For the actual treatment assignment, a patient is assigned to the placebo group if the patient only received placebo doses. If a patient received at least one dose of active IMP, the actual treatment received for the patient will be the active IMP treatment group.

#### **3.4. Per-Protocol Analysis Set**

The per-protocol (PP) analysis set is a subset of the ITT analysis set including only patients that did not experience any important protocol deviation prior to LoAC (if any) or the end of the treatment period, whichever comes first. The list of important deviations identified as having the potential to influence and/or bias the primary efficacy results are:

- Receive any dose of study drug by error, eg. randomized to receive test IMP but received dose(s) from placebo IMP, versa vise
- Did not complete planned study treatments (8 doses in total) for reason other than LoAC related
- Use of prohibited medications

A complete list of important deviations resulting in exclusion of patients from the PP analysis will be determined and documented at the end of the study based on a team review of accumulated blinded study data.

### **3.5. Pharmacokinetic Analysis Set**

The pharmacokinetic analysis set will include those patients in the safety analysis set who have at least 1 measurable concentration of TEV-48574.

## **4. GENERAL ISSUES FOR DATA ANALYSIS**

### **4.1. General**

Descriptive statistics for continuous variables include count (n), mean, SD, standard error (SE), median, minimum, and maximum. In addition, for TEV-48574 concentration, percentage coefficient of variation (%CV) and geometric mean will also be calculated. Descriptive statistics for categorical variables include patient counts and percentages, and a missing category will be displayed as appropriate.

Summaries of potentially clinically significant abnormal values for clinical laboratory tests and vital signs values will include all postbaseline values (including scheduled, unscheduled, and early withdrawal visits).

### **4.2. Specification of Baseline Values**

Unless otherwise noted, the baseline for clinic visit variables will be the last observed value before the first dose of study drug. The baseline for absolute eosinophil count will be the average of measurements prior to the administration of the first IMP.

The baseline for hand-held spirometry parameters and e-diary variables will be the average of the values over the 7 days preceding day of randomization.

### **4.3. Handling Withdrawals and Missing Data**

For all safety variables, only the observed data from the patients will be used in the statistical analyses, ie, there is no plan to estimate missing data, unless otherwise specified.

Dates that have incomplete information (the month and year or just the year is available) will be estimated for the purpose of calculating variables that are dependent on time if necessary. Day will be estimated as the first day (01) of the month (if month and year of partial date are available) or middle (July 1) of the year (if only year is available), unless otherwise noted. The imputations for partial dates are only for calculation purpose. Original date variables will not be modified. Listings will list dates as collected.

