7.1.2. Recording and Reporting of Adverse Events

For recording of adverse events, the study period is defined for each patient as the time period from signature of the ICF through the EOS visit. The period for reporting treatment-emergent adverse events is defined as the period after the first dose of IMP is administered and until the EOS visit.

All adverse events that occur during the defined study period must be recorded both on the source documentation and the CRF, regardless of the severity of the event or judged relationship to the IMP. Serious adverse events (Section 7.1.5) and/or PDAESI requiring reporting to GPSP (Section 7.1.6) must be reported within 24 hours from the investigator's awareness, using the SAE/PDAESI form (Section 7.1.5.3.1). The investigator does not need to actively monitor patients for new adverse events after the study period defined above.

All device-related adverse events, malfunctions etc. will be recorded and evaluated for their impact relative to the safety and efficacy of the IMP.

At each contact with the patient, the investigator or designee must question the patient about adverse events by asking open-ended questions such as “Have you had any unusual symptoms or medical problems since the last visit? If yes, please describe.” A precise diagnosis should be recorded whenever possible. When such a diagnosis is made, all related signs, symptoms, and any test findings will be recorded collectively as a single diagnosis on the CRF and, if it is a serious adverse event, on the serious adverse event form. Reported or observed signs and symptoms that are not manifestations of a known diagnosis should be reported individually.

The clinical course of each adverse event will be monitored at suitable intervals until resolved, stabilized, or returned to baseline; or until the patient is referred for continued care to a health care professional; or until a determination of a cause unrelated to the IMP or study procedure is made.

The onset and end dates, duration (in case of adverse event duration of less than 24 hours), action taken regarding IMP, treatment administered, and outcome for each adverse event must be recorded both on the source documentation and the CRF.

The relationship of each adverse event to the IMP and to the device, as well as the severity and seriousness of each adverse event, as judged by the investigator, must be recorded as described below.

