### **8.3. Adverse Events**

Adverse events will be recorded from time informed consent is obtained through the end of study participation.

All adverse events will be coded using MedDRA. Each patient will be counted only once in each preferred term or SOC category for the analyses of safety. Summaries will include treatment-emergent adverse events which are defined as adverse events occurring at or after the first dose of the IMP through the end of the follow-up visit. Listings will include all adverse events recorded.

Summaries will be presented for all adverse events (overall and by severity), adverse events determined by the investigator to be related to test IMP (defined as related or with missing relationship) (overall and by severity), adverse events determined by the investigator to be related to the medical device, or the study inhaler (defined as related or with missing relationship), serious adverse events, and adverse events causing drug withdrawal or discontinuation from the study. Adverse events with the missing flag indicating serious will be excluded from the summary of serious adverse events but included in the summary of non-serious adverse events.

Summaries for clinical asthma exacerbation related adverse events, loss of asthma control related adverse events, injection site reaction adverse events, protocol-defined adverse events of special interest (PDAESI), PDAESI require completion of suspected anaphylaxis will also be presented.

Listings for deaths, serious adverse events, adverse events leading to drug withdrawn or the study discontinuation, clinical asthma exacerbation related adverse events, loss of asthma control

related adverse events, injection site reaction adverse events, PDAESI, and PDAESI require completion of suspected anaphylaxis, adverse event required concomitant or additional treatment will be presented. In addition, listings for MedDRA dictionary terms for adverse event descriptions and adverse event preferred terms by patient number and treatment group will be presented.

Adverse events for patients who did not meet screening criteria will be listed.

In additional, adverse events and serious adverse events occurred during the 10 weeks period after the last dose of IMP will be summarized using descriptive statistics. These adverse events will be presented in a patient listing as well. Injection Site Assessments

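### SAP 4.3 sets a missing day to 01 with no exception for adverse-event onset, so a missing-day event in the first-dose month is classed as pre-dose and leaves the treatment-emergent summaries

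*SAP*

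**What the plan says.** SAP 4.3 gives one general rule for incomplete dates. They "will be estimated for the purpose of calculating variables that are dependent on time if necessary". When only the day is missing: "Day will be estimated as the first day (01) of the month (if month and year of partial date are available"). When day and month are both missing, the rule is "or middle (July 1) of the year (if only year is available), unless otherwise noted". The imputation affects derived variables only: "Listings will list dates as collected".

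SAP 8.3 says: "Adverse events will be recorded from time informed consent is obtained through the end of study participation". Its summaries cover treatment-emergent events, defined as "adverse events occurring at or after the first dose of the IMP through the end of the follow-up visit". Protocol 7.1.2 agrees in substance: "the period after the first dose of IMP is administered and until the EOS visit". On the untabulated data, SAP 8.3 adds: "Listings will include all adverse events recorded".

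Neither SAP 8.3 nor any other section of the SAP or protocol notes a different rule for a partial adverse-event onset date, or says how to class an event whose timing relative to first dose cannot be determined.

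**The concern.** Events are collected from consent, so the onset date alone decides whether an event counts as pre-dose or treatment-emergent. An event known only to have started in the month of first dose is ambiguous. Day-01 imputation resolves the ambiguity toward pre-dose for every patient not dosed on the 1st.

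That is the non-conservative direction for safety. It also runs against the choice SAP 8.3 makes for missing causality, where an event with missing relationship is counted as related.

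What is at stake is the incidence by treatment group. The summaries supply those figures, and the listings do not replace them. With 124 to 174 patients planned, a single event can be visible in a low-frequency row.

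**Working it through.** The plan gives no figure on this point to reproduce, so the check applies the rule directly.

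**Rule.** Imputed onset = day 01 of the recorded month (SAP 4.3). The event is treatment-emergent if imputed onset ≥ first-dose date (SAP 8.3).

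**Worked cases, day missing**

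| First dose | True onset | Imputed onset | Classed as |
|---|---|---|---|
| 15 March | 20 March | 1 March | pre-dose (wrong) |
| 1 March | 20 March | 1 March | treatment-emergent |
| 15 March | 2 April | 1 April | treatment-emergent |

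Only the first-dose month is affected. There, every missing-day event is lost unless dosing was on the 1st. In a 365-day year, 365 − 12 = 353 first-dose dates (96.7%) are exposed.

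**Share of events lost.** Inputs: an event window of study days 1 to 169 (end-of-study visit, SAP Table 1), and every first-dose date in 2021. Assumption: dosing dates and onsets are uniform over these days.

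- Pairs of dosing day and onset day, with onset on or after dosing in the same month of m days: m(m+1)/2. Summed over the year: 7 × 496 + 4 × 465 + 406 = 5,738.
- Of these, pairs with dosing on the 1st (kept): 365. Pairs lost: 5,738 − 365 = 5,373.
- All pairs: 365 × 169 = 61,685.
- Share of the window in the first-dose month: 5,738 / 61,685 = 9.3%.
- Lost, of missing-day events in that month: 5,373 / 5,738 = 93.6%.
- Lost, of all treatment-emergent events with a missing day: 5,373 / 61,685 = 8.7%.

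Enumerating first doses from July 2020 to September 2021 instead gives the same 9.3%, 93.6% and 8.7%. The 93.6% is below 96.7% because patients dosed on the 1st have the whole month ahead of them and so carry more event-days.

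**Share of all treatment-emergent events.** The frequency of partial onset dates is not in the documents. Assuming 1% to 3%: 0.01 × 8.7% = 0.09%, and 0.03 × 8.7% = 0.26%. Losing three events at the 3% end would need about 3 / (0.03 × 0.0871) ≈ 1,150 treatment-emergent events. That is about 7 per patient with 174 patients (1,150 / 174) or 9 with 124 (1,150 / 124).

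**Year-only dates.** First dose 15 September 2021, onset recorded as 2021: imputed 1 July, so a truly treatment-emergent event is lost. First dose 15 March 2021, true onset in February, recorded as 2021: imputed 1 July, so a pre-dose event is counted as treatment-emergent. The error can go either way.

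**After the fix.** If a partial onset whose known parts match the first dose is set to the first-dose date, the share of truly treatment-emergent missing-day events lost falls from 8.7% to 0%.

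**The case against.** The best case against the point has three parts.

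- **Scope.** SAP 4.3 opens by saying that safety variables use observed data only unless otherwise specified, and partial dates are estimated only where needed. The one section that refers back to the rule is asthma history (SAP 5.3). This does not exempt adverse events: the date rule follows in the same section, is worded generally, and covers any time-dependent variable. If it did not apply, the SAP would have no rule at all for classing a partial onset. Either reading calls for a sentence.
- **Rarity.** Protocol 7.1.2 requires onset dates. Adverse events are asked about at every visit, generally two weeks apart during treatment (Protocol Table 3), and missing data are queried (Protocol Appendix H). This stands, and it is why the effect is probably very small. A year-only onset is barely plausible in a study of about 30 weeks.
- **Visibility.** Lost events remain in the listings with their dates as collected. This also stands, but group incidences are taken from the summaries.

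A reader might also infer that the rule hides reactions to the loading dose. The documents do not support this. Local tolerability is assessed on site 1 and 2 hours after the first two doses, and the standard site findings and pain are not captured as adverse events (Protocol 7.6). Suspected anaphylaxis and hypersensitivity have a dedicated case report form (Protocol 7.1.6). Serious events are reported within 24 hours on a form that asks for the onset date (Protocol 7.1.5.3.1). These are the events least likely to lack a day.

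**Conclusion.** The point holds as a minor specification gap. Followed literally, SAP 4.3 and 8.3 together give the wrong class to a treatment-emergent event with a missing day in the first-dose month, unless dosing fell on the 1st. About 94% of such events, or about 9% of all treatment-emergent events with a missing day, leave the summaries. Those shares assume uniform dosing dates and onsets. Clustering of events soon after first dose would raise the 9% in proportion to the share falling in the first-dose month. At an assumed 1% to 3% of partial dates, the loss is about 0.1% to 0.3% of treatment-emergent events, so a loss of several events should not be expected.

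It would be too strong to say that the rule always understates treatment-emergent events. That is true of missing-day dates only; the 1 July rule can err in either direction.

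**What to change.** Add one sentence to SAP 8.3 before database lock: an adverse event with a partial onset date counts as treatment-emergent unless the available date parts or the stop date show onset before the first dose. For calculation, where the known parts match those of the first dose, and nothing shows earlier onset, impute the first-dose date.

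Leave SAP 4.3 as it is for medication and history dates. Extending the first-dose rule to medication start dates would do harm. SAP 6.4.4 takes inhaled corticosteroid use, with its baseline of 28 or 7 days before randomization, from the prior and concomitant medication data. Moving a partial start date to the first dose could erase run-in exposure from that baseline.

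The change affects no efficacy analysis and no trial conduct. Its cost is that an occasional pre-dose event, from screening or run-in, may be counted as treatment-emergent, which is the conservative direction for safety.

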### **4.4. Study Days and Visits**

For by-visit summaries, if there are multiple assessments at a postbaseline visit then the last non-missing assessment at that visit will be used for the summary (this includes scheduled and unscheduled assessments), except for triplicate ECG assessments (see Section 8.9 for further details).

Study visits are in [Table 1](#). See the study protocol Table 2 to 4 for details.

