- ^m In cases of a suspected severe systemic hypersensitivity reaction (eg, anaphylaxis), CAE, LoAC, serious adverse event or immunogenicity-related adverse event, efforts should be made to collect additional sample(s) for immunogenicity, serum total and free TL1A and serum concentration of TEV-48574. In cases of suspected or confirmed anaphylaxis, efforts should be made to collect samples for ADA determination as close to the onset of the event as possible, at resolution, and 30 days after onset of the event.
- ⁿ On signing the appropriate ICF, an optional blood sample may be collected for pharmacogenomics analysis.
- ^o If during administration or during post-IMP administration observation the patient develops clinical symptoms or signs, vital signs should be collected and a physical exam (brief or full, at the discretion of the investigator) performed. The patient should be assessed for anaphylaxis/hypersensitivity reactions as detailed in Section 7.1.6. IMP will be discontinued in patients who experience LoAC and background therapy will be restarted/increased; these patients will stay in the study.
- ^p All device-related adverse events, malfunctions etc. will be recorded and evaluated for their impact relative to the safety and efficacy of the IMP.
- ^q Administration site findings and pain will be assessed 1 hour after the completion of IMP administration. Additionally after the loading dose and first maintenance dose, assessments will also be performed 2 hours after the completion of administration. Allowed time windows for the local tolerability assessments are ± 15 minutes.

ADA=anti-drug antibody; ACQ-6=Asthma Control Questionnaire 6-question version; β -HCG=beta human chorionic gonadotropin; CAE=clinical asthma exacerbation; COVID-19=coronavirus disease 2019; DoR=day of randomization; ECG=electrocardiogram; EOT=End of Treatment; FeNO=fractional exhaled nitric oxide; ICF=informed consent form; ICS+LABA=inhaled corticosteroids + long acting beta-agonists; IMP=investigational medicinal product; LoAC=loss of asthma control; PK=Pharmacokinetic; random=randomization; SABA=short-acting beta agonist; V=visit.

Table 4: Study Procedures and Assessments: Follow-up Period

Study period	Follow-up
Visit number	V11 EOS
Procedures and assessments week after randomization - study day	24 169
Allowed time window, ±days	7
Concomitant medication inquiry	X
Adverse events inquiry	X
Perform COVID-19 symptoms inquiry ^a	X
LoAC and CAE inquiry	X

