Patients who continue to meet all of the inclusion criteria, none of the exclusion criteria, and all of the randomization criteria will be assigned a permanent unique randomization number and a treatment number generated by interactive response technology (IRT). These two newly assigned numbers will be entered into the CRF, and study drug will be dispensed. During the double-blind treatment period, patients will return to the study center every 2 weeks for administration of IMP, assessments and procedures.

The following procedures/assessments will be performed during and after administration of study drug:

- Administer IMP [REDACTED] using the [REDACTED]
- [REDACTED]
- Evaluation of local tolerability at the administration site at 1- and 2-hours post-administration.
- If, during administration or during post-IMP administration observation the patient develops clinical symptoms or signs, vital signs should be collected and a physical exam (brief or full, at the discretion of the investigator) performed. The patient should be assessed for anaphylaxis/hypersensitivity reactions as detailed in Section 7.1.6.

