3.6.1.2.3. Treatment Visit 3 (Week 4)

At this study visit, patients who have not had LoAC will begin the structured withdrawal of their background asthma controller therapies.

Efforts should be made to perform the following assessments and procedures in the order listed:

- Perform concomitant medication inquiry.
- Perform adverse event inquiry.
- Perform COVID-19 symptoms inquiry.

- Review daily e-diary for SABA/quick-relief medication usage and nighttime awakenings, including for adherence.
- Review daily hand-held spirometry, including for adherence.
- Perform LoAC and CAE inquiry.
- Patients who have not had LoAC will commence the structured withdrawal of their background asthma controller therapies (see Section 3.1).
- Complete the ACQ-6.
- Check supply and, if required, dispense study-provided controller therapies. Collect returned inhalers.
- Check supply of study-provided SABA. Collect returned inhalers.
- Perform ECG.
- Perform vital signs measurements (includes systolic and diastolic blood pressure, pulse, body temperature, and respiratory rate).
- Perform brief physical examination.
- Measure FeNO.
- Perform in-office spirometry (full flow-volume loop).
- Perform urine pregnancy testing (women of childbearing potential).
- Collect samples for clinical laboratory tests (serum chemistry, CBC with differential count, peripheral eosinophil count).
- Collect blood for serum TEV-48574 concentration determination (PK assessment) from all patients.
- Collect blood sample for immunogenicity (ADA) assessment.
- Collect blood sample for [REDACTED] assessment.

The following procedures/assessments will be performed during and after administration of study drug:

- Administer IMP [REDACTED] using the [REDACTED]
- [REDACTED]
- Evaluation of local tolerability at 1-hour post-administration.
- If, during administration or during post-IMP administration observation the patient develops clinical symptoms or signs, vital signs should be collected and a physical exam (brief or full, at the discretion of the investigator) performed. The patient should be assessed for anaphylaxis/hypersensitivity reactions as detailed in Section 7.1.6.

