3.6.1.2.4. Treatment Visit 4 (Week 6)

At this study visit, patients who have not had LoAC will continue the structured withdrawal of their background asthma controller therapies.

Efforts should be made to perform the following assessments and procedures in the order listed:

- Perform concomitant medication inquiry.
- Perform adverse event inquiry.
- Perform COVID-19 symptoms inquiry.
- Review daily e-diary for SABA/quick-relief medication usage and nighttime awakenings, including for adherence.
- Review daily hand-held spirometry, including for adherence.
- Perform LoAC and CAE inquiry.
- Patients who have not had LoAC will continue the structured withdrawal of their background asthma controller therapies (see Section 3.1).
- Complete the ACQ-6.
- Check supply and, if required, dispense study-provided controller therapies. Collect returned inhalers.
- Check supply of study-provided SABA. Collect returned inhalers.
- Perform vital signs measurements (includes systolic and diastolic blood pressure, pulse, body temperature, and respiratory rate).
- Perform brief physical examination.
- Measure FeNO.
- Perform in-office spirometry (full flow-volume loop).
- Perform urine pregnancy testing (women of childbearing potential).

The following procedures/assessments will be performed during and after administration of study drug:

- Administer IMP [REDACTED] using the [REDACTED]
[REDACTED]
- [REDACTED]
- Evaluation of local tolerability at the administration site at 1-hour post-administration.
- If, during administration or during post-IMP administration observation the patient develops clinical symptoms or signs, vital signs should be collected and a physical exam (brief or full, at the discretion of the investigator) performed. The patient should be assessed for anaphylaxis/hypersensitivity reactions as detailed in Section 7.1.6.

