7.6. Local Tolerability

Local tolerability assessments should be performed after each administration of IMP ([Table 3](#)) and include administration site findings and pain. Administration site findings (erythema, ecchymosis, induration, tenderness, warmth, and swelling) will be assessed using the scales provided in [Table 8](#). Pain at the administration site will be reported using a standardized 11-point pain intensity numerical response scale (NRS-11) where 0 is “No pain” and 10 is “Worst possible pain”. Patients will be asked to respond to the following question: “How much pain do you feel at the drug injection site?”

Both administration site findings and pain will be assessed 1 hour after the completion of IMP administration. Additionally after the loading dose and first maintenance dose, assessments will also be performed 2 hours after the completion of administration. Allowed time windows for the local tolerability assessments are ± 15 minutes.

Severity of local tolerability symptoms should be assessed as described in [Table 8](#). The surface diameter in millimeters should be recorded and erythema, induration, and ecchymosis at the administration site will be graded according to the diameter measurements: Absent, 5 mm to ≤ 50 mm (mild), >50 to ≤ 100 mm (moderate), and >100 mm (severe). Erythema, ecchymosis, and induration under 5 mm in diameter should be assessed as absent. Care should be taken to avoid pressuring or squeezing the administration site while assessing induration via careful superficial palpation.

In the case that findings do not resolve while the patient remains at the study center, additional evaluation should take place thereafter at each visit until resolution occurs. Administration sites

may be photographed, including between visits to the study center, to provide visual representation in addition to comments in the source documents. Any features that could be used to identify the patient will not be captured on the photograph. Appropriate treatment for administration site finding or pain may be provided if necessary, in which case such treatments must be recorded as concomitant medication(s).

Table 8: Administration Site Finding Severity Assessment

Test	Response
Erythema	- Absent - Erythema surface diameter 5 mm to ≤50 mm (mild) - Erythema surface diameter >50 to ≤100 mm (moderate) - Erythema surface diameter >100 mm (severe)

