**Table 2: Administration Site Finding Severity Assessment**

Test	Response
Erythema	- Absent - Erythema surface diameter 5 mm to ≤50 mm (mild) - Erythema surface diameter >50 to ≤100 mm (moderate) - Erythema surface diameter >100 mm (severe)
Ecchymosis	- Absent - Ecchymosis surface diameter 5 mm to ≤50 mm (mild) - Ecchymosis surface diameter >50 to ≤100 mm (moderate) - Ecchymosis surface diameter >100 mm (severe)
Induration	- Absent - Induration surface diameter 5 mm to ≤50 mm (mild) - Induration surface diameter >50 to ≤100 mm (moderate) - Induration surface diameter >100 mm (severe)
Tenderness Warmth Swelling	- None - Mild - Moderate - Severe

The injection site assessments (erythema, ecchymosis, induration, tenderness, warmth, and swelling) at each visit will be summarized using descriptive statistics. For NRS-11 scale, the worst pain score overall and the pain score at each visit will be summarized descriptively. The data will be listed using safety analysis set.

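### By-visit injection-site summaries use the 2-hour reading at Visit 2 (and possibly Visit 1) but the 1-hour reading at all later doses, so the columns are not comparable across doses

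*SAP*

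**What the plan says.** **Reading schedule.** Protocol 7.6 sets the common reading: "Both administration site findings and pain will be assessed 1 hour after the completion of IMP administration". It then adds a second one for two doses only: "Additionally after the loading dose and first maintenance dose, assessments will also be performed 2 hours after the completion of administration". Each reading has a window of ±15 minutes. Footnote q of Protocol Table 3 gives the same schedule. The visit lists in Protocol 3.6.1.2 agree: Visits 1 and 2 call for "Evaluation of local tolerability at the administration site at 1- and 2-hours post-administration", Visit 3 for "Evaluation of local tolerability at 1-hour post-administration", and Visit 4 for "Evaluation of local tolerability at the administration site at 1-hour post-administration". Visits 6 to 9 repeat the 1-hour line.

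**Selection rule.** For by-visit summaries, SAP 4.4 says that if there are "multiple assessments at a postbaseline visit then the last non-missing assessment at that visit will be used for the summary". The only exception it names is triplicate ECGs.

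**Planned summary.** SAP 8.3 summarises the six findings (erythema, ecchymosis, induration, tenderness, warmth and swelling) descriptively at each visit. For pain it says: "For NRS-11 scale, the worst pain score overall and the pain score at each visit will be summarized descriptively". It names no post-dose time and gives no rule of its own for choosing between two readings at one visit.

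**Adverse event capture.** Protocol 7.6 keeps the findings graded in its Table 8, and site pain, out of adverse event recording. Findings of other kinds, or findings that meet a seriousness criterion, are recorded.

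**The concern.** A by-visit tolerability table is naturally read from left to right: loading dose against maintenance doses, first exposure against repeat exposure. Here the time since injection changes at the same place in the table as the dose number. A difference between the early columns and the rest could reflect the drug, the dose number or the clock, and the table cannot separate them.

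Local tolerability is a stated safety endpoint (SAP 1.3), and Protocol 7.1.6 lists administration site reactions among the events of special interest, to be evaluated as in Protocol 7.6. Because the ordinary findings and pain are not adverse events, the SAP 8.3 table is their main summary. The rule also sets aside a planned reading at the doses where the protocol asked for closer observation.

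**Working it through.** No sample size, power or alpha is involved and the plan states no figure to reproduce. The check traces each dosing visit through the rule.

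| Visit | Dose | Readings planned (Protocol 7.6; 3.6.1.2) | Reading kept under SAP 4.4 |
|---|---|---|---|
| 1 | 1 (loading) | 1 h, 2 h | 2 h if Visit 1 counts as postbaseline; otherwise no rule |
| 2 | 2 | 1 h, 2 h | 2 h; 1 h if the 2-h value is missing |
| 3 | 3 | 1 h | 1 h |
| 4 | 4 | 1 h | 1 h |
| 6 | 5 | 1 h | 1 h |
| 7 | 6 | 1 h | 1 h |
| 8 | 7 | 1 h | 1 h |
| 9 | 8 | 1 h | 1 h |

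1. **Count.** A patient given all eight doses has 8 readings at 1 h and 2 at 2 h, 10 in all. A table with one value per visit shows at most 8. Six columns are at 1 h, one is at 2 h for certain, and one (Visit 1) is at 2 h or undefined.

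2. **The times are distinct.** With the ±15-minute windows, the readings fall at 45 to 75 minutes and at 105 to 135 minutes. They do not overlap.

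3. **Visit 1.** It is the day of randomization, and SAP 4.2 takes the baseline for clinic variables as the last value before the first dose. The post-dose readings come after baseline, but SAP 4.4 speaks of a postbaseline visit, and Visit 1 is also the baseline visit. The text supports either reading.

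4. **Mixing within a column.** Because the rule takes the last non-missing value, a patient with no 2-h reading at Visit 2 contributes the 1-h reading. The Visit 2 column can therefore hold both times.

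5. **Where the displaced 1-h reading can still be seen.** For the six findings, SAP 8.3 plans no worst-value summary, so a 1-h finding at Visit 2 with a 2-h value after it appears only in the listing. The same holds at Visit 1 if the rule reaches it. A 1-h pain score can still enter the worst score overall, but not the by-visit pain summary.

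6. **Direction.** Let p be the share with a finding at 1 h, r the share of those that resolve by 2 h, and d the share of patients without the finding at 1 h who have it by 2 h. Then the 2-h rate is p(1 − r) + (1 − p)d, and 2-h minus 1-h is (1 − p)d − pr. The documents give none of p, r or d. Purely as an assumption, take p = 20%. The difference is zero when d = 0.20r/0.80 = r/4. For assumed r of 25%, 50% and 75%, that is d = 6.25%, 12.5% and 18.75%. Below that d the early columns look too low; above it they look too high. The sign cannot be settled from the documents.

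7. **Between arms.** Both arms follow the same schedule at each visit, so scheduled reading time is balanced within a column.

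**The case against.** The best defence is that little is at stake. SAP 4.4 clearly reaches only Visit 2. SAP 8.3 plans descriptive summaries by treatment group, with no trend test or contrast between doses. Visit 1 carries the loading dose and later visits the maintenance dose, so those columns may not be alike in any case. All readings are listed, worst pain overall is summarised, and SAP 8.3 summarises injection-site-reaction adverse events and events of special interest separately. The last reading also has a coherent meaning: SAP 2.1 has patients observed for 2 hours after the first two doses and 1 hour after the rest, so it is status at the end of observation.

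Much of this stands as a limit on the consequence. It does not remove the problem. Visit 2 and Visits 3, 4 and 6 to 9 are all maintenance doses, yet their columns differ in reading time. The adverse event summaries do not cover ordinary findings and pain, which Protocol 7.6 keeps out. SAP 8.3 does not label its table as end-of-observation status, and the fallback to 1 h would break that meaning for some patients.

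Three stronger conclusions are tempting, and the documents do not support them:

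- A reader might infer that the table must show a false rise in reactions with repeat dosing. That needs findings to fade on balance between 1 h and 2 h, and a finding such as ecchymosis or induration may instead develop. No resolution or onset rate is given, so no fold-change can be claimed.
- A reader might infer that the drug-placebo comparison is biased. The shared schedule rules that out as far as scheduled reading time goes.
- A reader might infer that worst pain overall is faulty because early doses offer two readings. The maximum over all readings is a sound conservative safety summary, and both arms have the same planned opportunities. Restricting it to 1 h would discard observed 2-h pain.

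**Conclusion.** The point holds in a limited form. Applied as written, SAP 4.4 puts 2-h readings in the Visit 2 column and 1-h readings in the columns for Visits 3, 4 and 6 to 9, and leaves Visit 1 either at 2 h or without a rule. That is one of eight columns for certain and two at most. Comparisons across doses are unreliable by an amount and in a direction that the documents do not allow one to state.

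This is a stated rule producing a table that is not like-for-like on a safety endpoint, rather than a mere missing detail. The effect is confined to descriptive tolerability output: the primary analysis, its one-sided alpha and the sample size are untouched. The conclusion assumes that SAP 4.4 is meant to apply to the SAP 8.3 by-visit summaries, which follows from its wording and its single exception.

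**What to change.** In SAP 8.3, state that local tolerability is exempt from the last-assessment rule in SAP 4.4, and that site findings and NRS-11 pain are tabulated by visit and nominal post-dose time: 1 h at all eight dosing visits (1 to 4 and 6 to 9), with 2 h as a separate row for Visits 1 and 2. This also settles Visit 1 and stops a missing 2-h value from being replaced by the 1-h value in the same cell. Leave the worst pain score overall as the worst over all readings.

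The cost is one sentence in the SAP and one extra table row. No new data are needed, since both readings are already scheduled; it is assumed that they are stored separately by time point.
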